**PROTOCOL AMENDMENT I (11 Dec 2017)**

**This amendment provides for the following protocol change:**

**Protocol Change #1**

Original Protocol

Binocular near visual acuity will be assessed at the 6-month visit only. The analysis plan consisted of tabulating 6-month binocular near visual acuity by treatment group.

Protocol Change

Binocular near visual acuity will be assessed at both the Randomization visit and the 6-month visit (section 3.2). The analysis plan was changed to calculate the proportion of participants with loss of best corrected near vision >1 logMAR line at 6 months (sections 1.1, 1.12, and 7.4.2).

Rationale for Change

Binocular near visual acuity is an important outcome to assess the safety of low-dose atropine. In order to interpret any change in binocular near visual acuity between randomization to six months, a baseline measure is needed at the time of randomization.

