695 during run-in phase, based on investigator judgment after review of compliance calendars  
696 and discussion with parent.  
697 • Refractive correction in each eye (single vision eyeglasses or contact lenses with any  
698 necessary adjustment for contact lens rotation and vertex distance) that meets the  
699 following criteria:  
700 ○ Myopia (by spherical equivalent) in both eyes must be corrected to within ±0.50 D of  
701 the investigator's cycloplegic measurement of refractive error.  
702 ○ Cylinder power in both eyes must be within ±0.50 D of the investigator's standard  
703 refraction technique, which can be based on a cycloplegic or non-cycloplegic  
704 refraction.

- 705 ○ Cylinder axis for both eyes must be within  $\pm 5$  degrees of the axis found on the  
706 investigator's refraction when cylinder power is  $\geq 1.00$  D or within  $\pm 15$  degrees  
707 when the cylinder power is  $< 1.00$  D.  
708 Measurement of refractive error for assessing the above criteria may be performed as an  
709 over-refraction or without refractive correction.
- 710 ● Best-corrected distance visual acuity in current correction meeting the following criteria:  
711 ○ 20/32 or better in each eye ( $\geq 76$  letters by E-ETDRS testing)  
712 ○ Interocular difference  $\leq 0.2$  logMAR ( $\leq 10$  letters by E-ETDRS testing)

713  
714 Treatment Groups

715 Participants are randomly assigned 2:1 to the following two treatment groups:

- 716 ● Atropine Group: 0.01% atropine eyedrops administered 1 drop to each eye daily in each  
717 eye for 24 months, followed by 6 months off atropine eyedrops
- 718 ● Placebo Group: Placebo eyedrops administered 1 drop to each eye daily in each eye for  
719 24 months, followed by 6 months off placebo eyedrops

720  
721 Sample Size

722 Approximately 186 participants will be randomized in a 2:1 ratio to the two treatment groups  
723 (~124 in the atropine group and ~62 in the placebo group).

724  
725 Visit / Contact Schedule (*timed from randomization unless otherwise specified*)

- 726 ● Enrollment into run-in phase using daily artificial tear eyedrops for 2-4 weeks (and  
727 glasses updated if required)
- 728 ● Randomization Visit (2-4 weeks after enrollment)
- 729 ● Phone Calls from site: after 2 weeks ( $\pm 3$  days), and after 3, 9, 15, 21, and 27 months ( $\pm$   
730 1 month)
- 731 ● Office Visits:
  - 732 ○ 6 months  $\pm 2$  weeks\*
  - 733 ○ 12 months  $\pm 2$  weeks\*

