#### 1137 **4.9 Follow-up Visit Testing Procedures**

1138 At each office visit the following tests and assessments will be done with the participant wearing  
1139 their current refractive correction:  
1140

- 1141 1. Medical History - including questioning about the occurrence of adverse effects of treatment.  
1142 Concomitant medications will be recorded, as well as current eyeglasses or contact lenses  
1143 correction.
- 1144 2. Compliance Assessment
  - 1145 • All unused study medication ampules since the last visit (if brought to the visit) will  
1146 be counted as a measure of compliance.
  - 1147 • Home calendar logs (if brought to the visit) will be reviewed and assessments of  
1148 compliance with eyedrops and with refractive correction will be recorded on the  
1149 Follow-up Examination Form

- 1150 3. Eye Drop Questionnaire (all follow up visits except the 30-month visit)  
1151 • To be completed by the child prior to any other testing to evaluate the effect of eye  
1152 drops on the child.
- 1153 4. Distance Visual Acuity Testing (30-month visit only): Monocular distance visual acuity  
1154 tested at the start of the exam without cycloplegia in current correction.  
1155 • Measurement of best corrected visual acuity in each eye by a study certified visual  
1156 acuity tester using the E-ETDRS testing protocol.  
1157 • If the vision is more than one line ( $\geq 5$  letters) worse than baseline, retest using trial  
1158 frames or phoropter with the most recent subjective refraction.
- 1159 5. Binocular Near Visual Acuity Testing (6-month visit only): Binocular near visual acuity is  
1160 measured using the ATS4 Near Acuity Test with participant wearing current refractive  
1161 correction prior to administration of cycloplegia.
- 1162 6. Binocular Amplitude of Accommodation: Measured in their current correction without  
1163 cycloplegia with a study-specified and provided accommodation near-point rule (e.g.  
1164 Gulden's near-point rule).
- 1165 7. Standard Refraction  
1166 • The investigator may use their standard refraction technique (with or without  
1167 cycloplegia) at any time during the visit to ensure that refractive correction meets  
1168 study criteria at each visit (see section 4.9 below).  
1169 • At 30-month visit, only required if the vision is more than one line ( $\geq 5$  letters)  
1170 worse than baseline.
- 1171 8. Following cycloplegia, at all visits an examiner masked to treatment group will perform:  

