1172 • Cycloplegic Autorefraction – (see section 2.4)  
1173 • Cycloplegic Axial Length Measurement and Additional Biometry (see section 2.4)  
1174

1175 If a virtual visit is completed, only items 1 through 3 above will be completed. If any safety events  
1176 are identified during a virtual visit, participants will have additional follow up as applicable.  
1177

1178 In addition, females who have experienced menarche will undergo a urine pregnancy test at each  
1179 follow up visit except the 30-month visit (or at home if a virtual visit is completed).  
1180

- 1181 • In the case of pregnancy during the study, study eyedrops will be discontinued although  
1182 the subject will be retained in the study.  
1183

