### **7.4.2 Visual Acuity**

The proportion of participants with loss of best corrected distance vision >1 logMAR line at 30 months in either eye will be compared between treatment groups using Barnard's test. The proportion of participants with loss of best corrected near binocular vision >1 logMAR line at 6 months will be compared between treatment groups using Barnard's test.

1549 **7.5 Need for Bifocals**

1550 The proportion of participants needing bifocals in both groups will be evaluated.

1551

1552 **7.6 Interim Analysis**

1553 As specified by the DSMC, the decision of whether an interim analysis will be conducted will be  
1554 evaluated after 6 months of recruitment and before any outcome data is reviewed. An interim  
1555 monitoring plan will be developed at that point if circumstances warrant.

1556

1557 **7.7 Data Tabulations and Other Analyses**

1558 The following tabulations will be performed according to treatment group:

- 1559 • Baseline demographics and clinical characteristics
- 1560 • A flow chart accounting for all participants for all visits and phone calls
- 1561 • Visit and phone contact completion rates for each follow-up visit
- 1562 • Protocol deviations

1563

1564 **7.8 Sample Size**

1565 **7.8.1 General Considerations**

1566 The goal of this section is to summarize data from prior studies of myopia progression, use these  
1567 data to formulate assumptions about the expected treatment effect and its standard deviation, and  
1568 to calculate the sample size needed to provide at least 90% power for each of the 2 hypothesis  
1569 tests corresponding to the 24-month on treatment (primary) and 30-month off-treatment  
1570 secondary objectives.

1571

1572 To collect more safety data from participants using atropine, sample size was based on a 2:1  
1573 allocation (2 participants will be randomized to the atropine group for every 1 participant  
1574 randomized to the placebo group).

1575

1576 **7.8.2 Sample Size for Primary Objective: Efficacy on Atropine Treatment**

1577

1578 **Comparison of SER at 24 months**

1579 Sample size calculations for the on-treatment comparison of refractive error at 24 months were  
1580 based upon data from the CLEERE group and ATOM1 for untreated participants meeting similar  
1581 eligibility criteria, and data from participants treated with atropine 0.01% in the ATOM2 study.  

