1649 treatment effect) between 24 and 30 months (0.25D), then the estimated progression rate  
1650 between baseline and 30-months in the atropine group is 0.75D (0.50D at 24 months plus 0.25D  
1651 between 24 and 30 months). Compared with the estimated 1.25D progression rate in the placebo  
1652 group between baseline and 30-months (based on CLEERE data), the treatment group difference  
1653 would be expected to be 0.50D in favor of the atropine group.

1654  
1655 Assuming a slightly larger standard deviation of 0.90D at 30-months, and using a 2-sided t-test  
1656 with  $\alpha = 0.05$ , a sample size of 156 participants (104 in the atropine group and 52 in the  
1657 placebo group) is needed to detect a mean difference in SER (atropine – placebo) at 30 months  
1658 with 90% power, if the magnitude of the true mean difference is 0.50D or larger (Table 1).  
1659 Accounting for up to 15% loss to follow-up over 30 months, the sample size *for this objective* is  
1660 186 participants overall (124 in the atropine group and 62 in the placebo group) under this  
1661 scenario.

1662  
1663 **7.8.4 Summary of Sample Size Estimation**

1664 To be conservative, sample size for the study was chosen based upon the comparison of SER at  
1665 30 months (secondary objective) assuming that atropine group participants will progress at the  
1666 same rate as placebo between 24 and 30 months and that expected treatment group difference  
1667 between baseline and 30 months will be 0.50D, the scenario which has the largest sample size  
1668 requirement.

1669  
1670 The total sample size for the study will be 186 participants (124 in the atropine group and 62 in  
1671 the placebo group).

1672  
1673 **7.8.5 Precision within Racial Subgroups**

1674 Table 2 below summarizes the expected  $\frac{1}{2}$ -width of a 2-sided 95% confidence interval on the  
1675 treatment group difference of myopia progression for the exploratory analysis within subgroups  
1676 defined by race/ethnicity with an overall sample size of 156 participants completing the 30-  
1677 month primary outcome exam.

1678  
1679 For example: if participants of East Asian race/ethnicity make up 25% of the total sample (26 in  
1680 atropine group and 13 in placebo group) and the standard deviation of progression in this group

1681 is 0.80D, then the expected width of 2-sided 95% confidence interval for the treatment group  
 1682 difference in East Asians is  $\pm 0.55D$ .

1683

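### The trial's only post-randomization near-acuity comparison is a yes/no cut at more than one logMAR line, which detects a modest shift spread over many children poorly; add a difference in mean near acuity beside it

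*Protocol*

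**What the plan says.** Protocol section 7.4.2 sets both the endpoint and the test. The endpoint is the "proportion of participants with loss of best corrected near binocular vision >1 logMAR line at 6" months, and the two groups are compared on it by Barnard's test. Chapter 7 contains no other analysis of near acuity.

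Near acuity is measured with the ATS4 Near Acuity Test at the randomization visit (section 3.3, item 3) and once afterwards. Section 4.9, item 5 reads "Binocular Near Visual Acuity Testing (6-month visit only): Binocular near visual acuity is" measured in current correction before cycloplegia. The protocol does not say whether the result is recorded in whole lines or more finely. If the 6-month visit is virtual, the measurement is lost: "If a virtual visit is completed, only items 1 through 3 above will be completed", and near acuity is item 5.

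Protocol Amendment I, Change #1, which added the randomization measurement, gives the reason: "Binocular near visual acuity is an important outcome to assess the safety of low-dose atropine", with a baseline needed to interpret change.

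Other information on near function is collected. Section 4.9, item 6 is "Binocular Amplitude of Accommodation: Measured in their current correction without" cycloplegia, done at office visits, although Chapter 7 plans no analysis of it. There are also the eye drop questionnaire (7.4.1), adverse-event questions on near blur and reading difficulty (6.1), and the need for bifocals (7.5).

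**The concern.** A measurement taken on a logMAR scale at two times is reduced to one yes/no variable. A child who loses exactly one line is counted the same as a child who gains a line, and the baseline is used only to place the cut. That sits badly with the purpose Amendment I gives for collecting the baseline.

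An antimuscarinic drop could plausibly affect near vision through a small loss in many children. Table 2 in section 1.7 lists impaired near visual acuity at 0.5% and 0.1% and minimally reduced accommodation at 0.01%, which is compatible with a diffuse effect at the study dose. If that is the form the effect takes, a non-significant result on the cut could be taken as reassurance although the data already collected would have shown the shift.

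**Working it through.** **The plan's own figure.** The protocol states no power or expected rates for near acuity. Its sample size comes from refractive error at 30 months (section 7.8.3): difference 0.50 D, SD 0.90 D, two-sided 5%, 90% power, allocation 2:1. Placebo n = (1 + 1/2) × (1.960 + 1.282)² × 0.90²/0.50² ≈ 51.1, so 52, giving 104:52 = 156. With 15% loss, 52/0.85 = 61.2, so 62, and 3 × 62 = 186. This matches "186 participants overall (124 in the atropine group and 62 in the placebo group) under this" scenario.

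**Inputs for near acuity.**
- From the protocol: 124 atropine, 62 placebo; loss of more than one line; Barnard's test.
- Assumed: two-sided 5% (stated for refractive error, not for this test); normally distributed change; a mean shift of 0.05 logMAR (half a line); SD of change 0.08 to 0.15.
- Two scorings, because none is stated. Whole-line: more than one line means two or more lines, so the change must round to at least 0.2 and the cut is c = 0.15. Finer: c = 0.10.

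**Planned test.** Event rates are p(placebo) = 1 − Φ(c/SD) and p(atropine) = 1 − Φ((c − 0.05)/SD). At SD 0.10:
- whole-line: 1 − Φ(1.5) = 6.7% against 1 − Φ(1.0) = 15.9%; exact Barnard power 41%;
- finer: 1 − Φ(1.0) = 15.9% against 1 − Φ(0.5) = 30.9%; power 61%.

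**Comparison of mean change.** SE = SD × √(1/124 + 1/62) = 0.10 × 0.1556 = 0.01556. The noncentrality is 0.05/0.01556 = 3.21 on 184 df, against a critical value of 1.97. Power ≈ Φ(3.21 − 1.97) = Φ(1.24) ≈ 89%. With whole-line rounding, power comes from simulation.

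| SD | Whole-line: planned test | Whole-line: mean change | Finer: planned test | Finer: mean change |
|---|---|---|---|---|
| 0.08 | 43–44% | 94–96% | 74% | 98% |
| 0.10 | 40–41% | 84–87% | 61% | 89% |
| 0.12 | 36–37% | 71–74% | 49% | 76% |
| 0.15 | 28–29% | 53–56% | 35% | 57% |

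The whole-line ranges cover rounding the change once or rounding both readings, plus simulation error. The difference between the two analyses runs from about 22 points (57 − 35) to about 53 points (96 − 43).

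**Is Barnard's test the cause?** No. With 104:52 and SD 0.10, Barnard's test has 37% (whole-line) and 53% (finer), and a large-sample approximation for two proportions gives 35% and 52%. The power is lost at the cut.

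**Fewer evaluable children.** At 104:52 and SD 0.10, mean change has 83% against the 37% and 53% above. Virtual 6-month visits would act in the same direction.

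**Larger shift.** For a full line (0.10 logMAR), the planned test has about 99% power at SD 0.10 under either scoring, and 87% (whole-line) or 91% (finer) at SD 0.15.

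**Effect confined to a few children.** Suppose 10% of atropine children lose 0.2 logMAR and the rest lose nothing, with whole-line scoring at 124:62. Planned test against t-test on change: 54% against 28% at SD 0.07, about 38–40% against 24% at SD 0.08, and 22% against 18% at SD 0.10. Here the cut does better.

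**The case against.** The strongest objection is that the ranking depends on the shape of the effect. The evidence the protocol cites for 0.01% includes isolated cases (section 1.7: one of near blur, one of irritation), and a safety analysis may most want to find a susceptible minority. For that pattern, under whole-line scoring with SD up to about 0.10, the cut is the better test. This stands, and it rules out replacing the planned comparison or reducing it to description.

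A cut beyond one line also has some support. Amendment III, Change #5 places 0.1 logMAR within test-retest variability, although for distance E-ETDRS testing. That justifies caution in judging one child; a comparison of group means averages such noise out.

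A reader might infer that a half-line loss would usually be missed. Under whole-line scoring, power is below 50% at every SD tried from 0.05 to 0.20. With finer scoring it is 61% to 81% at SD 0.10 down to 0.07, so the inference fails there, and the protocol does not state the scoring. Nor does the protocol say that a half-line mean loss matters clinically; it is a benchmark chosen for this check.

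A reader might also infer that Barnard's test is a poor choice, or that the trial has no other evidence on near function. Neither follows: the test performs as it should on the proportions it is given, and accommodation amplitude, the questionnaire, adverse-event questions and bifocal need are all collected. None of these is near acuity, however.

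Finally, section 7.4.2 is a safety comparison that was not powered, and Chapter 7 is a framework for a later SAP that may already add a mean comparison. That limits the weight of the point.

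**Conclusion.** The point holds as a cheap improvement, not as an error. Section 7.4.2 analyses the only post-randomization near-acuity measurement solely through a cut at more than one line. For a diffuse half-line shift, this costs about 22 to 53 percentage points of power relative to comparing mean change. The figure rests on 124:62 children, two-sided 5%, normal change and an assumed SD of 0.08 to 0.15; the direction is the same under both scorings. It does not extend to an effect confined to a small subset, and it makes little practical difference for a full-line shift at SD up to about 0.10.

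**What to change.** In section 7.4.2, keep the comparison of the proportion losing more than one line as planned. Add the treatment-group difference (atropine − placebo) in 6-month binocular near acuity in logMAR, with a 95% CI, from an ANCOVA adjusted for near acuity at randomization, or a rank-based version if the scale is coarse or shows a ceiling. State how the near test is scored, and that a non-significant result on the cut is not to be read alone as evidence of no near-vision effect. If the SAP already contains this estimate, no change is needed.

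The cost is one or two sentences, with no new data, visits or participants. The downside is one more safety comparison, on a scale less direct for clinicians than a proportion.

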### 1616 7.8.3 Sample Size for Secondary Objective: Efficacy off Atropine Treatment

#### 1617 Comparison of SER at 30 months

1618 In CLEERE, the mean progression after 36 months was 1.50D in 127 untreated participants  
 1619 (95% CI = 1.34 to 1.66 D) with a SD of 0.89D (95% CI = 0.79 to 1.02 D). If the rate of  
 1620 progression in our study is similar (approximately 0.25D every 6 months), then the progression  
 1621 rate between baseline and 30-months in placebo participants is estimated to be 1.25D.  
 1622

1623 In ATOM2, the 71 participants who stopped atropine at 24 months progressed a mean of 0.28D  
 1624 (SD = 0.33D) after 12 months off treatment (95% CI for mean change = 0.20 to 0.36 D); and  
 1625 their mean progression from baseline to 36 months was 0.72D (95% CI = 0.55 to 0.89 D) with  
 1626 SD of 0.72D (95% CI = 0.62 to 0.86 D).  
 1627

1628  
 1629 If atropine group participants progress at the same rate as ATOM2 participants between 24 and  
 1630 30 months

1631 If atropine participants progress at the same rate as ATOM2 participants between 24 and 30  
 1632 months (estimated to be about 0.125 D over six months), then the estimated progression rate

1633 between baseline and 30-months in the atropine group is 0.625D (0.50D at 24 months plus  
1634 0.125D between 24 and 30 months). Compared with the estimated 1.25D progression rate in the  
1635 placebo group between baseline and 30-months (based on CLEERE data), the treatment group  
1636 difference would be expected to be 0.625D in favor of the atropine group.

1637  
1638 Assuming a slightly larger standard deviation of 0.90D at 30-months, and using a 2-sided t-test  
1639 with  $\alpha = 0.05$ , a sample size of 102 participants (68 in the atropine group and 34 in the  
1640 placebo group) is needed to detect a mean difference in SER (atropine – placebo) at 30 months  
1641 with 90% power, if the magnitude of the true mean difference is 0.625D or larger (Table 1).  
1642 Accounting for up to 15% loss to follow-up over 30 months, the sample size *for this objective* is  
1643 120 participants overall (80 in the atropine group and 40 in the placebo group) under this  
1644 scenario.

1645  
1646 *If atropine group participants progress at the same rate as placebo participants in CLEERE*  
1647 *between 24 and 30 months*

1648 If atropine participants progress at the same rate as placebo participants in CLEERE (i.e. no  
1649 treatment effect) between 24 and 30 months (0.25D), then the estimated progression rate  
1650 between baseline and 30-months in the atropine group is 0.75D (0.50D at 24 months plus 0.25D  
1651 between 24 and 30 months). Compared with the estimated 1.25D progression rate in the placebo  
1652 group between baseline and 30-months (based on CLEERE data), the treatment group difference  
1653 would be expected to be 0.50D in favor of the atropine group.

1654  
1655 Assuming a slightly larger standard deviation of 0.90D at 30-months, and using a 2-sided t-test  
1656 with  $\alpha = 0.05$ , a sample size of 156 participants (104 in the atropine group and 52 in the  
1657 placebo group) is needed to detect a mean difference in SER (atropine – placebo) at 30 months  
1658 with 90% power, if the magnitude of the true mean difference is 0.50D or larger (Table 1).  
1659 Accounting for up to 15% loss to follow-up over 30 months, the sample size *for this objective* is  
1660 186 participants overall (124 in the atropine group and 62 in the placebo group) under this  
1661 scenario.

1662  
1663 **7.8.4 Summary of Sample Size Estimation**

1664 To be conservative, sample size for the study was chosen based upon the comparison of SER at  
1665 30 months (secondary objective) assuming that atropine group participants will progress at the  
1666 same rate as placebo between 24 and 30 months and that expected treatment group difference  
1667 between baseline and 30 months will be 0.50D, the scenario which has the largest sample size  
1668 requirement.

1669  
1670 The total sample size for the study will be 186 participants (124 in the atropine group and 62 in  
1671 the placebo group).

1672  
1673 **7.8.5 Precision within Racial Subgroups**

1674 Table 2 below summarizes the expected  $\frac{1}{2}$ -width of a 2-sided 95% confidence interval on the  
1675 treatment group difference of myopia progression for the exploratory analysis within subgroups  
1676 defined by race/ethnicity with an overall sample size of 156 participants completing the 30-  
1677 month primary outcome exam.

1678  
1679 For example: if participants of East Asian race/ethnicity make up 25% of the total sample (26 in  
1680 atropine group and 13 in placebo group) and the standard deviation of progression in this group

1681 is 0.80D, then the expected width of 2-sided 95% confidence interval for the treatment group  
 1682 difference in East Asians is  $\pm 0.55D$ .

1683

1684 **Table 2. Expected width of 2-sided 95% confidence interval on the treatment group**  
 1685 **comparison of myopia progression as a function of the standard deviation of progression**  
 1686 **and sample size per race/ethnicity subgroup\***

Race/Ethnicity Subgroup as Proportion of Total Sample Size	Standard Deviation of Mean SER Change from Baseline** (D)						
	0.8	0.9	1.0	1.1	1.2	1.3	1.4
10% n=15	$\pm 0.95$	$\pm 1.06$	$\pm 1.18$	$\pm 1.30$	$\pm 1.42$	$\pm 1.54$	$\pm 1.66$
20% n=30	$\pm 0.63$	$\pm 0.71$	$\pm 0.79$	$\pm 0.87$	$\pm 0.95$	$\pm 1.03$	$\pm 1.11$
25% n=39	<math>\pm 0.55</math>	$\pm 0.62$	$\pm 0.69$	$\pm 0.76$	$\pm 0.83$	$\pm 0.89$	$\pm 0.96$
30% n=48	$\pm 0.49$	$\pm 0.55$	$\pm 0.62$	$\pm 0.68$	$\pm 0.74$	$\pm 0.80$	$\pm 0.86$
40% n=63	$\pm 0.43$	$\pm 0.48$	$\pm 0.53$	$\pm 0.59$	$\pm 0.64$	$\pm 0.69$	$\pm 0.75$
50% n=78	$\pm 0.38$	$\pm 0.43$	$\pm 0.48$	$\pm 0.53$	$\pm 0.57$	$\pm 0.62$	$\pm 0.67$
60% n=93	$\pm 0.35$	$\pm 0.39$	$\pm 0.44$	$\pm 0.48$	$\pm 0.52$	$\pm 0.57$	$\pm 0.61$
70% n=108	$\pm 0.32$	$\pm 0.36$	$\pm 0.40$	$\pm 0.45$	$\pm 0.49$	$\pm 0.53$	$\pm 0.57$
80% n=126	$\pm 0.30$	$\pm 0.34$	$\pm 0.37$	$\pm 0.41$	$\pm 0.45$	$\pm 0.49$	$\pm 0.52$
90% n=141	$\pm 0.28$	$\pm 0.32$	$\pm 0.35$	$\pm 0.39$	$\pm 0.42$	$\pm 0.46$	$\pm 0.49$

1687

1688 \*Cells show the expected  $\frac{1}{2}$ -width of 2-sided 95% confidence interval on the treatment group comparison of myopia  
 1689 progression as a function of the standard deviation of progression and sample size per race/ethnicity subgroup.

1690

1691 \*\*The range of standard deviation was based on the standard deviation of progression in CLEERE group data at 36-  
 1692 months, stratified by race/ethnicity group. At 36 months, the standard deviations of progression in Asian, Black,  
 1693 Hispanic, and White populations were 1.02D (95% CI =0.82 to 1.36D), 0.61D (95% CI =0.47 to 0.88D), 0.82D  
 1694 (95% CI =0.67 to 1.05D), and 0.92D (95% CI =0.70 to 1.36D) respectively.

1695

